Features of AE registration in some cases:

Lack of preventive effect

Absence of preventive effect of therapy should not be registered as AE.

Pregnancy

All cases of pregnancy that developed in the participants of the clinical trial against the background of the study therapy during the period of participation in the study are subject to mandatory registration in the Pregnancy Registration Form and are not accompanied by the registration of AE/SAE. The signed and dated pregnancy form is sent to LLC "NPP "Pharmaclon" by e-mail: [contact] , - within 5 working days from the date of notification of the research doctor.

AE in the period before taking study drug

In the presence of deviations of laboratory, physiological and/or instrumental indicators at the screening or randomization visit before the first use of the drug, in the future, the following are subject to registration as AE:

- all deviations accompanied by an increase in severity according to the version used;
- deviations that are not associated with a change in severity, but have, from the researcher's point of view, clinical significance.

If the participant had deviations of laboratory, physiological and/or instrumental indicators at the visit before the first use of the study drug, after which the indicators during the study normalized or the severity of the deviation changed for the better, and then changed again for the worse, but the values of the indicators remained within the same severity according to If the patient was on a visit before the first use of the study drug, the phenomenon should not be registered as AE, except in cases where it is clinically significant from the point of view of the research physician.

Registration of a disease/syndrome characterized by several symptoms

In case of registration of a disease accompanied by various symptoms, registration of individual symptoms as AE is not required, however, it is recommended to list all the symptoms of the disease in the note to the description of the AE.

For more detailed information on the procedures for registration and evaluation of adverse events under this Protocol, see the Guide on Adverse Events Version 2 of 17/02/2021.

QUALITY CONTROL

Direct access to primary data/documentation

The researcher/research center is obliged to provide direct access to primary data/documentation for examination by the Ethics Council under the Ministry of Health of the Russian Federation, an Independent Ethics Committee, as well as inspections by authorized bodies. Ethics Council/The Independent Ethics Committee, the authorized bodies, and the sponsor of this study, to the extent permitted by law, will have direct access to the original medical records of the participant to verify the procedures and/or research data, without violating the confidentiality of the participant's data. By signing the Information Sheet with the informed consent form, the Participant gives permission for such access.

Inspection

National regulatory authorities may conduct inspections during and after the study.

Accounting of drugs

The researcher or other responsible persons will keep records of the study drug.

The researcher is responsible for the fact that the study drugs:

- stored in proper conditions in a lockable and safe place;
- scheduled, and the registration of drugs is documented with the indication of the number of the participant to whom the drug was issued.

The control of the study drugs should be documented throughout the study.

Storage of drugs

The Ingaron® preparation should be stored in a dry place protected from light, at temperature no higher than +25 ° C. Ingaron® solution should be stored for no more than 10 days in the refrigerator (do not freeze).

All participants will be instructed by the researcher about the required storage conditions when receiving study drug at visit 1.

RESEARCH DOCUMENTATION

Storage of documentation

The researcher undertakes to keep all documentation on the study, including the original medical documentation of the participants (outpatient records, diaries) for 15 years after the completion of the study. This documentation regarding the ongoing research should be available for audits and inspections by regulatory authorities.

STATISTICAL METHODS

Populations for analysis

During the statistical analysis, the following populations of participants will be studied:

- ❖ All participants included in the study (FAS, Full Analysis Set). This population will be used to describe basic characteristics, including demographic and anthropometric indicators, data on concomitant diseases, and will also be used as the main population to assess performance parameters. In this case, the participant's group will be determined by the "intention to treat" (ITT Analysis).
- ❖ Auxiliary analysis of effectiveness parameters is planned for all subjects who completed the study without significant deviations from the study protocol (PP, Per Protocol).

Methods of descriptive statistics

For numerical indicators, such as demographic and anthropometric data (body weight, age, height, BMI), as well as numerical performance parameters will be calculated:

- Number of missing values (N);
- Minimum value (Min);
- Maximum value (Max);
- Arithmetic Mean (M);
- Standard Deviation (SD);
- 95 % confidence interval (CI) for the mean;

- Median (Me).

For qualitative variables (frequency of AE/SAE development, for example), absolute number in the n/N format will be given, as well as the percentage (%).

Analysis of basic characteristics

The distribution of subjects, demographic and baseline characteristics will be presented using descriptive statistics methods for all subjects included in the study (FAS-population). An intergroup comparison of the basic quantitative characteristics will be carried out using the t-test (or the Mann-Whitney test), depending on the type of data distribution. For categorical data, the χ^2 -criterion or Fisher's exact test will be applied if the expected frequency in any of the cells is less than 5.

Standard methods available in the XLSTAT 2020.3 program will be used for data analysis.

When analyzing numerical data, preliminary testing of variables for the normality of the distribution will be carried out using Shapiro-Wilk's test, as well as a test for asymmetry and kurtosis with an indication of the p value when testing the null hypothesis of the normal distribution of the variable. In the case of a normal distribution, an intra-group comparison of parameter changes is carried out using a paired t-test. For a comparative evaluation, the χ^2 -criterion or the exact Fisher test will be used if the expected frequency in any of the cells is less than 5.

Significance level

A significance level of 0.05 will be used in all tests. Correction for the multiplicity of comparison is not introduced.

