- to evaluate the safety of the proposed regimen of preventive therapy with Ingaron (INN: human recombinant interferon gamma, lyophilizate for the preparation of solution for intranasal administration of 100,000 IU) in adult volunteers. Safety is assessed based on adverse events, clinically significant changes in laboratory parameters during the study, taking into account the assessment of severity according to the STCAE 4.03 scale.

OBJECTIVES OF NON-INTERVENTIONAL RESEARCH

Primary objective

To evaluate the effectiveness of the prophylactic use of Ingaron (INN: human recombinant interferon gamma, lyophilizate for the preparation of solution for intranasal administration of 100,000 IU) in the mode of 3 drops in each nasal passage intranasally every other day for 10 days with break of 7 days (2 10-day cycles) in adult volunteers.

Secondary objectives

Safety assessment of the prophylactic use of Ingaron (INN: human recombinant interferon gamma; lyophilizate for the preparation of a solution for intranasal administration of 100,000 IU), applied 3 drops into each nasal passage intranasally every other day for 10 days with break of 7 days (two 10-day cycles) in adult volunteers.

Efficacy and safety include evaluation based on epidemiological, anamnestic, and clinical data, as well as laboratory studies and specialized scales.

DESIGN OF A NON-INTERVENTIONAL STUDY

Post-marketing prospective randomized open-label comparative non-interventional study in parallel groups.

A total of 4 visits are planned (0–3). Visit 0 and 1 can be combined.

Main stages of the study

1. Visit 0. Conducted in person⁷. Screening: informed consent, inclusion of volunteers and distribution into groups (Day -3-1)
2. Visit 1. Conducted in person. Randomization. Delivery of the investigated drug and the diary of the researcher participant (Day 0)
3. Visit 2. It is carried out remotely (by phone). Completion of a preventive course, evaluation of preventive efficacy and safety during the period of drug administration. The beginning of the observation period. (Day 28–30)
4. Visit 3. Conducted in person. Completion of the observation and research period. (Day 56–62)

The main procedures and stages of the study are reflected in the Schedule of research procedures.

The total duration of participation is about 2 months (56–62 days).

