For participants who have a case of ARVI (COVID-19), visit 3 can be carried out earlier or later, but the total duration of the study should not be more than 90 days. Up to this point, medical researcher should try to collect the most complete information about the patient's condition. If it is not possible to conduct a face-to-face visit, final visit is conducted remotely.

Schedule of research procedures

| Visit number | 0 | 1 | 2 | 3 |
|---|-----------|---------------|--|--|
| Setting | In person | In person | Phone call | In person |
| Visit name | Screening | Randomization | The end of the course of prevention Beginning of the observation period | End of the observation period Completion of the study |
| Study days | -3-1(0) | 0 | 27 (+/-3) | 56-62* |
| Informed consent ¹ | + | | | |
| Anamnesis ² | + | | | |
| Complaints | + | + | + | + |
| Physical examination ³ | + | + | | + |
| Pregnancy test | + | | | |
| Safety assessment | + | + | + | + |
| Analysis for RNA to SARS-CoV-2 ⁴ | + | | | + |
| Checking the inclusion/non-inclusion criteria | + | + | | |
| Checking exclusion criteria | | | + | |

⁷ A full-time visit can be carried out both at the research center and at home

| | | | | |
|--|---|---|---|----------------|
| Randomization | | + | | |
| Delivery of the study drug ⁵ | | + | | + |
| Compliance assessment | | | + | + |
| Issue of the participant's diary | | + | | |
| Effectiveness evaluation | | | + | + |
| Assessment of the participant's condition according to the WHO scale | + | + | + | + ⁷ |
| Return of study drug and diary | | | | + |

* For patients with a registered case of ARVI, duration of participation in the study may be longer, but not exceed 90 days

- 1 All research procedures, except routine laboratory and instrumental studies, the data of which are used to assess the condition of the study participant, are performed after the procedure of signing the informed consent of the patient
- 2 The study should indicate the epidemiological history of respiratory viral diseases, status of vaccination (influenza, pneumonia, COVID-19), use of means of nonspecific protection and prevention of acute respiratory viral infections, including COVID-19

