In case of a positive PCR test before the start of the drug, volunteer is not included in the study, is isolated and falls under the supervision of a district doctor. In case of a positive PCR test during or after the preventive course, volunteer continues to participate in the study, is isolated under observation and, if possible, comes to visit 3 after the quarantine is lifted (at least 14 days from the date of signing Consent for the treatment of a new coronavirus infection COVID-19 in outpatient conditions (at home) and observing the isolation regime or discharge from the hospital in case of laboratory confirmation of COVID-19) with the provision of data on their condition to the researcher coordinator.

STUDY POPULATION

Adult volunteers who do not have clinical symptoms of ARVI.

Inclusion criteria

1. Volunteers of both genders over 18 years old.
2. Obtaining a written form of informed consent.
3. Ability and consent to participate in this study.
4. No symptoms of respiratory infection.
5. A negative result of a PCR study for the presence of SARS-CoV-2 RNA according to the biomaterial obtained by nasopharyngeal ⁹smear.

Non-inclusion criteria

1. Any other concomitant diseases or conditions that, in the opinion of the research doctor, may distort the results of the study, restrict the rights of the volunteer, or put him at greater risk.
2. Contraindications to the use of the study drug.
3. Individual intolerance of the ingredients included in the composition of the study drug.
4. Pregnancy or breast-feeding.
5. Controversial result of PCR test for the presence of SARS-CoV-2 RNA according to the biomaterial obtained by nasopharyngeal smear.
6. Participation in a clinical trial using the investigated therapy for 30 days prior to inclusion in this study.
7. Disagreement on following reliable contraceptive measures in the framework of the study

⁹ It is permissible to accept the results of a nasal or pharyngeal smear, as well as the results of studies performed before inclusion in the study for no more than 72 hours.

(sexual abstinence; or a combination of 2 different methods: for example, barrier and spermicides, or barrier and intrauterine device, or barrier and hormonal, etc.) – for participants with preserved childbearing potential.

Number of participants

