1. The proportion of patients with confirmed COVID-19 at the end of the period of preventive treatment of the drug (measurement period: 28 days).
2. The proportion of patients with acute respiratory viral infections, including COVID-19, at the end of the follow-up period (change period: 2 months).
3. The proportion of patients with confirmed COVID-19 at the end of the follow-up period (change period: 2 months).
4. Frequency of development of complicated course of ARVI.
5. The proportion of participants with each of the scores (0-8) according to the WHO Clinical Improvement Scale (change period: 28 days).
6. The proportion of participants with each of the scores (0-8) according to the WHO Clinical Improvement Scale (change period: 2 months).
7. Duration of symptoms of the disease of study participants who had acute respiratory viral infections, including COVID-19 (change period: 2 months).
8. The duration of the symptoms of the disease of the study participants who were infected with ARVI, including COVID-19 (measurement period: 28 days).

Confirmation of clinical cases of ARVI, including COVID-19:

In the following cases:

- 1) a positive result of PCR on SARS-CoV-2 RNA, regardless of the presence of clinical symptoms;
- 2) appearance of clinical symptoms of ARVI in the absence of a PCR result on SARS-CoV-2 RNA or in the case of a negative result on SARS-CoV-2 RNA, -

at any stage during participation in the study, a completion visit (Visit 3) is conducted at the end of the quarantine period (at least 14 days from the date of signing Consent for the treatment of a new COVID-19 coronavirus infection in outpatient settings (at home) and compliance with the isolation regime or discharge from the hospital in case of laboratory confirmation of COVID-19), at which the patient returns the participant's diary and reports his condition to the doctor-researcher, transmits information about hospitalization, duration of symptoms, results of tests and performed studies.

Definition of the COVID-19 case:

Suspicious case of COVID-19

Body temperature above 37.5° in addition to one or more of the following signs (in the absence of other known causes that explain the clinical picture, regardless of the epidemiological history):

- Cough (dry or with scant sputum)
- Shortness of breath
- Feeling of congestion in the chest
- SpO₂ no more than 95%
- Sore throat
- Nasal stuffiness or moderate rhinorrhea
- Smell disorders or anosmia
- Ageusia
- Conjunctivitis
- Fatigue

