5.3. Missing / incorrect data

For all parameters, the analysis will be carried out only on the available information, without filling in the data. There are no plans to use data reconstruction methods in this study.

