5.5. Populations of participants for analysis

The following populations will be formed for analysis: ITT, PP and safety; additionally: ITT_NV, PP_NV, ITT_NV_BE, PP_NV_BE.

Statistical data analysis will be carried out in the following populations of participants:

1. Population of all included and randomized participants (intention-to-treat, ITT): all randomized participants who were exposed to the study drug, regardless of the degree of protocol compliance during the study. This data set is the main one for the analysis of primary and secondary effectiveness parameters;
2. Population of participants who completed the study according to the protocol (per protocol, PP): all randomized subjects who completed participation in the study in accordance with the protocol (completed the prescribed period of treatment and follow-up without significant deviations from the protocol). This data set is additional for the analysis of primary and secondary effectiveness parameters;
3. Safety population: The data set analyzed for safety assessment is identical to the ITT data set. However, unlike the population depending on the prescribed treatment, participants are analyzed depending on the actual treatment (if it differs from the treatment that was prescribed by randomization). All types of safety analysis will be based on the use of a data set for security assessment;
4. Modified population of all included and randomized participants (intention-to-treat, ITT) not vaccinated against COVID-19: ITT_NV. This data set is additional for the analysis of the primary efficiency parameter;
5. Modified population of participants who completed the study according to the protocol (per protocol, PP), not vaccinated against COVID-19: PP_NV. This data set is additional for the analysis of the primary efficiency parameter;
6. Modified population of all included and randomized participants (intention-to-treat, ITT) not vaccinated against COVID-19 or vaccinated before inclusion in the study: ITT_NV_BE. This data set is additional for the analysis of the primary efficiency parameter;
7. Modified population of participants who completed the study according to the protocol (per protocol, PP), not vaccinated against COVID-19 or vaccinated before inclusion in the study: PP_NV_BE. This data set is additional for the analysis of the primary efficiency parameter.

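### An ARVI can bring the completion visit forward with no earliest day set, so follow-up of early-onset cases depends on the outcome; secondary endpoints and possibly the PP set are exposed, the ITT Day 28 primary endpoint is not

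*Protocol*

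**What the plan says.** Visit 3 is planned for Day 56–62 (protocol, Main stages of the study). The schedule table labels it as the end of the study. Drug and diary are returned there, and it carries the only SARS-CoV-2 PCR scheduled after screening.

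For participants who fall ill, the documents give several different rules:

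- Protocol, text after Main stages: "visit 3 can be carried out earlier or later, but the total duration of the study should not be more than 90 days".
- Protocol, Confirmation of clinical cases, repeated in SAP 3.2: after a positive PCR, or ARVI symptoms with a negative or absent PCR, "at any stage during participation in the study, a completion visit (Visit 3) is conducted at the end of the quarantine period". Quarantine is put at 14 days or more, counted from signing the consent to home COVID-19 treatment, or until hospital discharge where COVID-19 is laboratory-confirmed.
- Protocol, schedule footnote (asterisk): "For patients with a registered case of ARVI, duration of participation in the study may be longer, but not exceed 90 days".
- Protocol, end of the Nasopharyngeal smear section: "In case of a positive PCR test during or after the preventive course, volunteer continues to participate in the study".
- SAP 2.1: visits and procedures follow the same schedule for every participant.

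Two SAP rules bear on the consequences. SAP 5.5 defines PP as those who "completed the prescribed period of treatment and follow-up without significant deviations from the protocol". SAP 5.3 states that "the analysis will be carried out only on the available information, without filling in the data".

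**The concern.** A site that follows the case-confirmation text closes a participant out because of an ARVI, possibly weeks before non-cases are closed. A site that follows the footnote does not. Under the first reading, length of observation depends on the outcome, and so on the arm if the drug works.

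The items at stake are these:

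- **Confirmed COVID-19 at 28 days and 2 months.** A participant whose first illness is a PCR-negative cold has the Visit 3 PCR early. A later infection, including a symptomless one that counts as confirmed under the case definition, goes unseen.
- **WHO scores at 28 days and 2 months, and adverse-event follow-up.** These may be missing or mistimed only in people who fell ill, and nothing is filled in.
- **PP.** A case closed early might be judged not to have completed follow-up, and so be removed because it is a case.
- **Control-arm exposure.** Footnote 5 to the schedule lets controls receive a vial on completion, which for an early-closed control could fall inside the 28-day or 2-month window.

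**Working it through.** **Planning rates.** The protocol's Number of participants section plans for up to 5% in controls and a reduction of at least 3 points, so 5% versus 2%. Its own formula with t = 1.96 gives (0.05×0.95 + 0.02×0.98)×1.96²/0.03² = 0.0671×3.8416/0.0009 = 286.4, which matches the stated 286 per group. Expected cases by Day 28 are 286×0.05 = 14.3 (control) and 286×0.02 = 5.7 (Group I).

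**Timing.** Visit 3 day = onset day + lag. The documents give a floor of 14 days. Assumptions: the lag starts at onset, onset is uniform over time, and the lag lies between 14 and 28 days.

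| Lag (days) | Visit 3 before Day 28 if onset before | Share of Day 0–28 cases | Control / Group I cases | Visit 3 before Day 56 if onset before | Share of Day 0–56 cases | Visit 3 after Day 62 if onset after |
|---|---|---|---|---|---|---|
| 14 | Day 14 | 50% | 7.2 / 2.9 | Day 42 | 75% | Day 48 |
| 21 | Day 7 | 25% | 3.6 / 1.4 | Day 35 | 63% | Day 41 |
| 28 | none | 0% | 0 / 0 | Day 28 | 50% | Day 34 |

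Example: onset on Day 5 gives Visit 3 from Day 19. That is 37 to 43 days short of Day 56–62 and just after Course 2 would start (10 + 7 days, so about Day 18).

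**Visit 2.** Main stages gives Day 28–30, but the schedule table gives 27 (+/-3), which opens on Day 24. Against Day 24 and a 14-day lag, only onset before Day 10 pre-empts the call: 10/28 = 36% of cases, about 5 control and 2 Group I.

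**Observation lost.** With a 14-day lag, cases arising by Day 28 lose on average 28 days against Day 56. That is 14.3×28 = 400 person-days in control, or 2.5% of 286×56 = 16,016, and 5.72×28 = 160 (1.0%) in Group I.

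**Second illnesses missed.** As an upper bound for these cases, let the whole ARVI risk recur in the lost time. Control: 286×0.05² = 0.7. Group I: 286×0.02² = 0.1. At the higher control incidences named in the protocol the bound is 286×0.08² = 1.8 and 286×0.18² = 9.3.

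**PP, if every case closed before Day 28 were dropped (14-day lag).** Control: (14.3 − 7.15)/(286 − 7.15) = 2.6%. Group I: (5.72 − 2.86)/(286 − 2.86) = 1.0%. The difference falls from 3 points to about 1.6; the ratio stays near 0.4.

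**The case against.** The strongest reply is that the primary result is safe, and that stands. The endpoint is binary at Day 28 and SAP 5.1 makes ITT the main analysis; anyone closed out because of an ARVI is already an event.

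Four further replies also stand, in whole or in part:

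- **Not all cases lose follow-up.** A reader might infer that they do. Only early-onset cases can be closed early, and with onset after about Day 48 a case is followed longer than non-cases, up to Day 90.
- **The clock is uncertain.** The 14 days run from a COVID-19 treatment consent or involve discharge after laboratory confirmation. For a PCR-negative cold no starting point is defined, so the Day 19 example is an assumption.
- **Loss of Course 2 is an inference.** No passage stops dosing at an ARVI, ARVI is not among the exclusion criteria, and PCR-positive volunteers continue. The inference rests only on drug return at Visit 3.
- **The halved PP difference is not established.** PP removes significant or critical deviations, and a Visit 3 held early as the protocol permits is arguably neither. The compliance scale scores one complete course at 80%, above the exclusion threshold of 50% or less. SAP 5.5 also makes PP additional, although the protocol's sample-size section calls it the primary analysis population.

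Nothing cancels the Visit 2 call for cases, and SAP 3.2 wants a WHO score at each visit. But nothing requires that call once Visit 3 has closed participation, so the conflict remains.

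**Conclusion.** The passages contradict each other, and followed literally they make follow-up, and the timing of the only scheduled post-baseline PCR, depend on the outcome. This should be fixed, but it does not threaten the ITT Day 28 primary result.

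The size is modest at the planning rates. About 7 control and 3 Group I cases could close before Day 28 if the lag is 14 days from onset and onset is uniform, about half that with 21 days and none with 28. Missed second illnesses among control cases arising by Day 28 number at most about 0.7 at 5% incidence; the bound matters only at incidences well above plan.

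PP rates of about 2.6% versus 1.0% are what would follow if PP dropped every case closed before Day 28. The SAP does not say whether it would, so a halved effect cannot be asserted. Nor do the documents support saying that cases in general forfeit their second course.

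**What to change.** 1. Reconcile the protocol's text after Main stages, the schedule footnote, the statement on PCR-positive volunteers, the case-confirmation section, and SAP 2.1 and 3.2. State that an ARVI may delay Visit 3, to at most Day 90, but may not bring it before Day 56.
2. Keep the Visit 2 call and the Day 56–62 assessment for cases as for non-cases, so that the 28-day and 2-month endpoints are read at the same times in everyone. Give Visit 2 one window in place of the two now stated.
3. In SAP 5.5, state that an ARVI, or visit timing changed because of it, is not a reason to leave PP.
4. The sponsor should reconcile the passages on whether study drug use continues after an ARVI. No dosing rule is proposed here.

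The cost is mainly wording in both documents; the sample size does not change. Some cases would attend Visit 3 a few weeks later than the text now allows, and end-of-illness data may need a telephone contact outside the four scheduled visits.
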